10.2 Handling Partial Dates or Missing Dates

10.2.1 Missing Date Information for Adverse Events

The following imputation rules only apply to cases in which the start date is incomplete (i.e., partially missing).

Missing day and month

- If the year is same as the year of the date of the first dose of double-blind study drug, then the day and month of the date of the first dose of double-blind study drug will be assigned to the missing fields.
- If the year is prior to the year of the date of the first dose double-blind study drug, then December 31 will be assigned to the missing fields.
- If the year is after the year of the date of the first dose double-blind study drug, then January 1 will be assigned to the missing fields.

Missing month only

- The day will be treated as missing and both month and day will be replaced according to the above procedure.

Missing day only

- If the month and year are same as the year and month of the date of the first dose double-blind study drug, then the date of the first dose double-blind study drug will be assigned to the missing day.
- If either the year is before the year of the date of the first dose of double-blind study drug or if both years are the same, but the month is before the month of the date of the first dose of double-blind study drug, then the last day of the month will be assigned to the missing day.
- If either the year is after the year of the date of the first dose of double-blind study drug or if both years are the same, but the month is after the month of the date of the first dose of double-blind study drug, then the first day of the month will be assigned to the missing day.

If the stop date is complete and the imputed start date as above is after the stop date, the start date will be imputed by the stop date.

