2.4 Study Design

This is a Phase 2, multicenter, stratified, randomized, double-masked, placebo-controlled study with a 4-week screening period, a 144-week treatment period, an optional 96-week open label sub-study, and a 4-week post-treatment follow-up period (either study completion or early termination). A minimum of 36 subjects with nonsense mutation aniridia who are ≥ 2 years of age are planned for enrollment into this study at investigator sites in US and Canada.

During the 4-week screening period, subjects will be assessed for eligibility.

Eligible subjects will enter the 144-week treatment period consisting of two stages:

- Stage 1 (Weeks 1 to 48) during which subjects will receive either ataluren or placebo in a masked fashion;
- Stage 2 (Weeks 49 to 144) during which subjects will receive open-label ataluren.

Eligible subjects will be randomized in a masked 2:1 fashion to either ataluren or placebo. Randomization will be stratified by age: ≤ 10 years versus > 10 years. Masked study drug will be dosed three times a day: 10 mg/kg in the morning, 10 mg/kg at midday, and 20 mg/kg in the evening for 48 weeks. Subjects (or parent/legal guardian) will record each dose on a diary card provided by PTC Therapeutics.

After completion of the Stage 1 (Week 48), subjects will be eligible for an additional 96 weeks of open-label ataluren treatment. Subjects who received ataluren during Stage 1 will continue to receive ataluren; subjects who had been randomized to placebo will receive ataluren during Stage 2

There will be an optional sub-study at the end of the Stage 2 Open-Label Extension. Subjects will be able to consent to receive an additional 96 weeks of ataluren treatment, returning to the clinic every 24 weeks. The assessments to be conducted are outlined in the schedule of events. Subjects who choose not to participate in the sub-study will be required to complete the Post-treatment follow-up visit at the end of the Stage 2 Open-Label Extension.

[figure not shown]
The start of the sub-study will require prior approval of a protocol amendment from applicable Institutional Review Boards and will continue for 96 week or until commercial availability of ataluren for this indication, whichever is first, or until a positive risk-benefit assessment in this indication is not demonstrated.

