The arithmetic difference between a post-baseline value and the baseline value:

Change from Baseline = (Post-baseline Value – Baseline Value)

Percentage Change from Baseline = [(Post-baseline Value – Baseline Value) / Baseline Value] x 100

End of Double-masked study period

End of double-masked study period is at Week 48 (day 337 ± 28 days), unless terminated early.

End of Study

End of study is at Week 144 (day 1008 ± 7 days), unless terminated early.

Early termination from study

Early termination would be assigned to the visit whose visit window included the termination date. In the event that an early termination visit does not fall within a nominal visit window, then the termination visit will be assigned to the visit closest to that date. If duplicate data result from the assignment of a termination visit, then the values measured last will be selected for analysis.

Enrollment date

Enrollment date will be assigned after confirmation of eligibility has been received from PTC Therapeutics, but not after the first day of study drug administration.

Study drug

Study drug in this study is ataluren (PTC124) or placebo.

Randomization date

Randomization date is the day the subject is assigned a randomization number on study Day 1.

Study Day 1

Day 1 is defined as the first day that study drug is administered to the subject.

Study Day

Day on study = Starting from Day 1

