7.5.1 Adverse Events

Adverse events will be grouped by system organ class and by preferred term within system organ class according to the latest version of the Medical Dictionary for Regulatory Activities coding dictionary. The number of subjects reporting at least 1 adverse event will be summarized by treatment group. Tables and/or narratives of any on-study death, serious or significant adverse events, including early withdrawals because of adverse events, will be provided should they occur.

Summary information (the number and percent of subjects by treatment) will be tabulated for:

- Treatment-emergent adverse events, including clinical and laboratory adverse events
- Treatment-related adverse events
- Treatment-emergent adverse events by severity
- Treatment-related adverse events by severity
- SAEs
- Adverse events leading to discontinuation
- Ocular adverse events

Adverse events will be summarized separately through Week 48 (Study Phase 1), from Week 48 through Week 148, through Week 148, and through end of treatment, including sub-study. Adverse events will be assigned to a study phase based on the start date of the adverse event. In study Stage 1 and entire study, AEs will be summarized by treatment. In addition, AEs while subjects are on ataluren will be presented for the entire study.

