Appendix A Schedule of Events

The types and timing of data to be recorded are summarized in Table 1 (Stage 1, double-masked period), Table 2 (Stage 2, open-label period), and Table 3 (open-label sub-study).

Table 1. Schedule of Events (Stage 1)

Protocol Activities		Screening				Double-Masked Treatment			
Day±Window	Week	-28	-4	1 ^a	1	169±28	24	337±28	48/ End of Stage 1 ^b
Visit		1		2		3			4
Informed consent		X							
Medical and ophthalmic history ^c		X							
Serum viral screen		X							
Physical exam		X		X					X
Height and weight		X		X		X			X
Vital signs		X		X		X			X
Ophthalmoscopy		X		X		X			X
Hematology, biochemistry, urinalysis		X				X			X
Serum β-HCG ^d		X		X		X			X
Study drug and diary dispensing				X		X			X
Study drug administration				X		X			X
Study drug compliance and return						X			X
Collect diary						X			X
Adverse events				X		X			X
Concomitant meds		X		X		X			X
MNREAD				X					X
████████████████████				X		X			X
Slit-lamp examination ^e				X		X			X
Slit-lamp photography				X		X			X
OCT				X		X			X
Fundus photography				X		X			X
Humphrey visual fields				X					X
BCVA (visual acuity and refraction) ^f		X		X		X			X
████████████████████				X		X			X
████████████████████				X		X			X
████████████████████ blood				X		X			X
sample for plasma PK ^g									If feasible (i.e., during surgery for glaucoma, cataracts, etc.)

Abbreviations: β -HCG, beta-human chorionic gonadotropin; BCVA, best corrected visual acuity; ETDRS, Early Treatment Diabetic Retinopathy Study; [REDACTED]; LEA, LEA Symbols Visual Acuity Test System; MNREAD, Minnesota Low Vision Reading (MNREAD) Acuity Charts; OCT, optical coherence tomography; PK, pharmacokinetic(s)

^a All study and laboratory assessments on the first day of treatment must be done prior to in-clinic administration of the first dose.

^b Open-label study drug administration will start at the end of Stage 1 (Visit 4/Week 48).

^c Should include capture of available historical values for ocular assessments included in this study, such as visual acuity, [REDACTED], etc.

^d Sample taken only for female subjects of childbearing potential.

^e Slit-lamp examination should precede [REDACTED] measurement.

^f Visual acuity and refraction will be assessed using the Early Treatment Diabetic Retinopathy Study (ETDRS) or an age-appropriate alternative (e.g., LEA).

Table 2. Schedule of Events (Stage 2)

Protocol Activities		Open-Label Treatment						End of Study)/ Early Termination ^a		Follow-Up ^b	

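### Partial adverse event dates are anchored only to the first double-blind dose, so placebo subjects' events of uncertain date around crossover drop out of the on-ataluren display

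*SAP*

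**What the plan says.** SAP 10.2.1 has three rules that matter here, and each refers to the first double-blind dose.

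- Day and month missing, same year as that dose: "If the year is same as the year of the date of the first dose of double-blind study drug, then the day and month" of that dose are filled in.
- Day and month missing, later year: "If the year is after the year of the date of the first dose double-blind study drug, then January 1 will be assigned".
- Day missing, later month: "then the first day of the month will be assigned to the missing day".

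One further rule uses the stop date: "If the stop date is complete and the imputed start date as above is after the stop date, the start date will be imputed" from the stop date. It acts only when the imputed start is too late, so it can move a start earlier but never later.

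The first open-label ataluren dose appears nowhere in these rules. Yet the study has a second treatment start: "subjects who had been randomized to placebo will receive ataluren during Stage 2" (SAP 2.4). SAP section 5 sets its time: "End of double-masked study period is at Week 48 (day 337 ± 28 days), unless terminated early". The footnotes to Table 1 in SAP Appendix A start open-label dosing at that visit.

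SAP 7.5.1 makes the start date decisive: "Adverse events will be assigned to a study phase based on the start date of the adverse event". The same section summarises events up to Week 48 and from Week 48 on, and adds a whole-study display of events that arose on ataluren. Week 48 closes one period and opens the next. The SAP does not say to which of them the crossover day belongs.

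**The concern.** For subjects randomised to placebo, Visit 4 is the first exposure to active drug. An event known only to the year or month of that visit could have begun on either side of it. The imputation rules settle the doubt the same way every time, by dating the event to the placebo period.

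This is the reverse of the SAP's choice at the first double-blind dose. There, a doubtful date in the same year or month is set to the dose date, so the event counts as on treatment. Elsewhere the plan does treat crossover as a new start: SAP 7.2 gives placebo subjects a Week 48 baseline for the combined ataluren summaries, and Protocol 11.8.2 gives them a second laboratory baseline.

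The rule can also override what the site knows. At Visit 5 (Protocol 8.1.1.5) sites record events that have arisen since the previous visit. A placebo subject's event recorded there as new, with only the year known, began after Visit 4. If that year is the crossover year, the rule still dates it to January 1 or to the first double-blind dose.

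At stake is the account of events on ataluren, which serves the secondary safety objective in a very small trial.

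**Working it through.** **Inputs.** The imputation rules are from SAP 10.2.1, the crossover day from SAP section 5, and phase assignment from SAP 7.5.1. Allocation is 2:1 (SAP 2.4). The sample size is 24 in SAP 2.5 but still 36 in SAP 7.1, so both are used.

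**Step 1: the stated crossover day.** 48 × 7 + 1 = 337, as the SAP says. With ±28 days, crossover falls between day 309 and day 365. The first open-label dose is taken to fall on the crossover day.

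**Step 2: the rules by case.** Crossover is at least 308 days after the first dose, so the crossover month is never the first-dose month.

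- Year only, crossover in the first-dose year: imputed to the first-dose date, which is before crossover.
- Year only, crossover in the next year: imputed to January 1, which is on or before crossover.
- Day missing, crossover month: imputed to the 1st, which is on or before crossover.

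No case gives a date after crossover.

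**Step 3: enumeration.** All first-dose dates in a four-year cycle (1,461) were combined with all 57 crossover days from 309 to 365: 1,461 × 57 = 83,277 combinations, equally weighted.

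| Partial date | Imputed before crossover | Tied with crossover | After crossover |
|---|---|---|---|
| Year only, crossover year | 83,049 (99.73%) | 228 (0.27%) | 0 |
| Day missing, crossover month | 80,541 (96.71%) | 2,736 (3.29%) | 0 |

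The ties are crossovers on January 1 or on the 1st of a month. No imputed date precedes the first dose, so every date before crossover lies in the placebo period. Crossover falls in the first-dose calendar year in 8.0% of combinations and in the next year in 92.0%.

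**Step 4: two examples (crossover on day 337).**

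- First dose 14 June 2017, crossover 16 May 2018: 1 January 2018 (year only) or 1 May 2018 (day missing).
- First dose 10 January 2017, crossover 12 December 2017: 10 January 2017 or 1 December 2017.

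All four imputed dates are in the placebo period.

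**Step 5: how often that is wrong.** Of the days that such a partial date allows, 50% (year only) and 52% (day missing) fall on or after crossover. Of those days, 99.5% and 93.6% are dated to the placebo period.

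**Step 6: what is not affected.** An event with a known later month of the crossover year, or a year-only event in a later year, is correctly dated after crossover; the enumeration found no errors among these.

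**Step 7: effect of one event.** Suppose the moved event is the subject's only event of its type.

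- On-ataluren display, both arms pooled, all placebo subjects crossing over: 1/24 = 4.2 points, or 1/36 = 2.8 points.
- Placebo Stage 1 rate: 24/3 = 8 subjects, 1/8 = 12.5 points; or 36/3 = 12 subjects, 1/12 = 8.3 points.

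**The case against.** The rule is complete, can be programmed as written, and contradicts no other section. Any convention misplaces some events, and about half of the doubtful days do belong to the placebo period. Few events should be affected: onset date is a required item (Protocol 9.3), events are collected at every visit including Visit 4, and a missed visit prompts a telephone call (Protocol 8.3.12). Adverse events are not tested statistically (Protocol 11.8). Subject listings are planned, as are tables or narratives for serious events and withdrawals.

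All of this stands and limits the weight of the point. It does not change the direction of the error in the on-ataluren display, and no other section corrects it.

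A reader might go further and infer that the rule lowers the ataluren rate in the Stage 1 comparison. The documents do not support that. A placebo subject's event after crossover never belonged to the ataluren arm in Stage 1, so moving it cannot lower that arm's rate. The same rule applies to subjects randomised to ataluren, whose Stage 2 events can also be pulled back into Stage 1. Stage 1 counts can therefore be inflated in both arms, and the net effect on the contrast is not determined.

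A reader might also size the loss as 1 in 16, the subjects randomised to ataluren when N = 24, or about 6 points. That denominator is wrong, because the display that loses the event pools both arms.

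**Conclusion.** The point holds for events on ataluren. A placebo-randomised subject's event known only to the crossover year, or only to the crossover month and year, is never dated after the first open-label dose. It therefore leaves the on-ataluren display and the post-Week 48 summary and joins the placebo Stage 1 count. The sole exception is a tie, which the SAP does not allocate. In the on-ataluren display the error runs one way, towards understatement. It is not a one-way bias in the Stage 1 comparison.

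The sizes in Step 7 are per event. They assume 2:1 allocation exactly met, N of 24 or 36, and, for the pooled display, that all placebo subjects cross over. The shares in Steps 3 and 5 assume evenly spread first-dose dates, crossover days and possible onset days. Neither document gives an expected number of incomplete dates, so the total effect cannot be computed; it is probably small. The change is still worth making because it is cheap and the groups are so small.

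**What to change.** Make three additions, two to SAP 10.2.1 and one to SAP 7.5.1.

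1. **On-ataluren display (10.2.1).** If the known part of a placebo-randomised subject's start date matches the year, or the month and year, of the first open-label ataluren dose, impute that dose date. Make an exception where the stop date or the recording visit shows that the event began earlier.
2. **Stage 1 versus Stage 2 split (10.2.1).** Apply one rule to both arms: bound the start date by the visit at which the event was first recorded, then impute within those bounds. The anchor in item 1 must not be used here. It would move doubtful events out of Stage 1 for placebo subjects only and make the comparison asymmetric. The recording visit is not among the items listed in Protocol 9.3, so the SAP should name the data field that supplies it.
3. **Crossover day (7.5.1).** State which phase it belongs to.

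Matching text for medication start dates in SAP 10.2.2.1 is optional, for consistency.

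The cost is a few lines of text and programming. The downside is that some events that truly began on placebo will be shown as on ataluren. That is the conservative direction the SAP already takes at the first double-blind dose, and the stop-date and visit checks limit it.

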10.2.2 Missing Date Information for Prior or Concomitant Medications

For prior or concomitant medications, including rescue medications, incomplete

(i.e., partial missing) start date and/or stop date will be imputed. When the start date and the stop date are both incomplete for a subject, impute the start date first.

10.2.2.1 Incomplete Start Date

The following rules will be applied to impute the missing numerical fields. If the stop date is complete and the imputed start date is after the stop date, then the start date will be imputed using the stop date.

Missing day and month

- If the year of the incomplete start date is the same as the year of the date of the first dose of double-blind study drug, then the day and month of the date of the first dose of double-blind study drug will be assigned to the missing fields.
- If the year of the incomplete start date is prior to the year of the date of the first dose of double-blind study drug, then December 31 will be assigned to the missing fields.
- If the year of the incomplete start date is after the year of the date of the first dose of double-blind study drug, then January 1 will be assigned to the missing fields.

Missing month only

- The day will be treated as missing and both month and day will be replaced according to the above procedure.

Missing day only

- If the month and year of the incomplete start date are the same as the month and year of the date of the first dose of double-blind study drug, then the day of the date of the first dose of double-blind study drug will be assigned to the missing day.
- If either the year is before the year of the date of the first dose of double-blind study drug or if both years are the same, but the month is before the month of the date of the first dose of double-blind study drug, then the last day of the month will be assigned to the missing day.
- If either the year is after the year of the date of the first dose of double-blind study drug or if both years are the same, but the month is after the month of the date of the first dose of double-blind study drug, then the first day of the month will be assigned to the missing day.

10.2.2.2 Incomplete Stop Date

The following rules will be applied to impute the missing numerical fields. If the date of the last dose of double-blind study drug is missing, replace it with the last visit date or data cut-off date if the subject is on-going. If the imputed stop date is before the start date (imputed or non-imputed start date), then the imputed stop date will be equal to the start date.

Missing day and month

- If the year of the incomplete stop date is the same as the year of the date of the last dose of double-blind study drug, then the day and month of the date of the last dose of double-blind study drug will be assigned to the missing fields.
- If the year of the incomplete stop date is prior to the year of the date of the last dose of double-blind study drug, then December 31 will be assigned to the missing fields.
- If the year of the incomplete stop date is after the year of the date of the last dose of double-blind study drug, then January 1 will be assigned to the missing fields.

Missing month only

- The day will be treated as missing and both month and day will be replaced according to the above procedure.

Missing day only

- If the month and year of the incomplete stop date are the same as the month and year of the date of the last dose of double-blind study drug, then the day of the date of the last dose of double-blind study drug will be assigned to the missing day.
- If either the year is before the year of the date of the last dose of double-blind study drug or if both years are the same, but the month is before the month of the date of the last dose of double-blind study drug, then the last day of the month will be assigned to the missing day.
- If either the year is after the year of the date of the last dose of double-blind study drug or if both years are the same, but the month is after the month of the date of the last dose of double-blind study drug, then the first day of the month will be assigned to the missing day.

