### 11.10 Concomitant Medication Use

Concomitant medications will be coded by means of the World Health Organization Drug Dictionary into Anatomical-Therapeutic-Chemical classification codes. The type and timing (between each visit) of use of specific concomitant medications will be listed and summarized.

The frequency, timing (between each visit), type, and amount of any other therapies for aniridia will be considered with special interest.

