7.5.5 Physical Examinations and Other Parameters

Height, weight, physical examination, ophthalmoscopy, slit-lamp examination, and visual fields will be summarized by visit using descriptive statistics over the course of the study. Medications taken prior to entering the study and started while on study (i.e., concomitant) will be summarized to Week 48, from Week 48 to Week 148, and through end of treatment, including sub-study.

7.6

[REDACTED]

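### SAP 10.2.2 date rules move a medication with only a start year, and a stop month earlier in the first-dose year, to Day 1, overwriting the recorded stop month

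*SAP*

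**What the plan says.** The rules are in three consecutive SAP sections.

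- **Order (SAP 10.2.2).** "When the start date and the stop date are both incomplete for a subject, impute the start date first".
- **Start date (SAP 10.2.2.1).** If day and month are missing and the year is the first-dose year, "then the day and month of the date of the first dose of double-blind study drug will be assigned to the missing fields". For an earlier year, 31 December of that year is used. One check pulls the start back to the stop: "If the stop date is complete and the imputed start date is after the stop date, then the start date will be imputed using".
- **Stop date (SAP 10.2.2.2).** A stop with a known month before the month of the last masked dose, day missing, becomes the last day of the recorded month. A stop that then precedes the start is reset to it: "If the imputed stop date is before the start date (imputed or non-imputed start date), then the imputed stop date will be equal".

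SAP 5 defines Day 1 as the first day of study drug. On use of the dates, SAP 7.5.5 states: "Medications taken prior to entering the study and started while on study (i.e., concomitant) will be summarized to Week 48", and for later periods. SAP 7.5.2 tabulates numbers and percentages of patients by stage and treatment group. Protocol 11.10 summarizes timing of use between visits and adds that the frequency, timing, type and amount of "any other therapies for aniridia will be considered with special interest". Protocol 7.1 counts as concomitant anything taken from the screening period through the 4-week follow-up.

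**The concern.** A stop recorded as March is real information: it excludes use in September whatever the start was. The SAP accepts this logic for a complete stop date but not for a stop that lacks only its day. In that case the order of steps reverses the weight of evidence. A guessed start is fixed first, and the partly recorded stop is then changed to agree with it.

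At stake is the line between prior and concomitant medication, and the timing attached to eye treatments. A drug finished before the study could be shown as a one-day drug taken on Day 1, only because the stop day was not written down. The arms are small. With the target of 24 in SAP 2.5, 2:1 allocation gives 16 and 8 subjects, so one misplaced drug can shift a placebo percentage by 1/8 = 12.5 points. With the 36 in SAP 7.1 it is 1/12 = 8.3 points.

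**Working it through.** The documents give no figure on this point, so the check is to apply the rules literally.

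**Worked record.** Assumed first dose 17 Sep 2018 and last masked dose 335 days later, 18 Aug 2019. Start recorded as 2018.

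| Step | Stop recorded as Mar 2018 | Stop recorded as 20 Mar 2018 |
|---|---|---|
| Start, year only, same year as first dose (10.2.2.1) | 17 Sep 2018 | 17 Sep 2018 |
| Check against a complete stop (10.2.2.1) | does not apply | start pulled back to 20 Mar 2018 |
| Stop, day missing (10.2.2.2) | 31 Mar 2018 | recorded |
| Stop before start? (10.2.2.2) | yes, so stop moved to 17 Sep 2018 | no |
| Result | start = stop = 17 Sep 2018 (Day 1) | start = stop = 20 Mar 2018 (before Day 1) |

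The stop moves forward by 30 + 31 + 30 + 31 + 31 + 17 = 170 days.

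**How far the stop moves.** Take every first-dose date in a non-leap year with every earlier stop month of that year, a year-only start and a month-only stop. The number of combinations is the sum over months m of (days in month m) × (m − 1):

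28×1 + 31×2 + 30×3 + 31×4 + 30×5 + 31×6 + 31×7 + 30×8 + 31×9 + 30×10 + 31×11 = 2017.

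All 2017 end with start and stop on Day 1. The stop moves by a median of 104 days, mean 117, maximum 334 (31 January to 31 December). The length of masked treatment does not matter: setting the last masked dose 0, 28 or 335 days after the first gives the same results.

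**Where the effect stops.** A second grid put the first dose on the 15th of each month of one year. It crossed this with all true start and stop month pairs from two years earlier, with the stop month before the first-dose month.

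| Recorded parts | Start year | Combinations reaching Day 1 |
|---|---|---|
| Start year only, stop month and year | first-dose year | 286 of 286 |
| Start year only, stop complete | first-dose year | 0 of 286 |
| Start month known, stop month and year | first-dose year | 0 of 286 |
| Start complete, stop month and year | first-dose year | 0 of 286 |
| Start year only, stop month and year | earlier year | 0 of 5184 |

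In the last row the stop is still pushed to 31 December of the earlier year in 1584 of 5184, but the drug stays prior. A January first dose cannot produce the effect, because no earlier month exists in that year.

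**Overlap with screening.** Screening is 4 weeks before baseline (Protocol 8.1.1.1). The imputed month-end stop lies within 28 days before first dose when the stop month is the one just before and dosing falls on days 1 to 28. That is 11 × 28 = 308 of 2017 (15%). Such drugs are likely already concomitant under Protocol 7.1, so their dates become wrong but their class may not change. In the other 2017 − 308 = 1709, the recorded month ended more than 28 days before first dose.

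**The case against.** Several points on the other side stand.

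- **The counts are not frequencies.** 2017 of 2017 and 286 of 286 are true by construction, since those grids contain only the failing pattern. They show that the rule always acts this way on that pattern, not how often the pattern occurs.
- **Use of the imputed dates is not spelled out.** SAP 5 has no date rule for prior versus concomitant, and SAP 7.5.2 and 7.5.5 name the categories without saying that imputed dates assign them. That use is likely, but it is an inference.
- **Few records may qualify.** Protocol 8.3.2 asks for current medications at Visit 1 and gives no look-back for drugs already stopped, although prior medication is to be summarized.
- **The override has a purpose.** With last masked dose 18 Aug 2019, start Oct 2019 and stop 2019, the rules give start 1 Oct 2019 and stop 18 Aug 2019. Moving the stop to the imputed start is what prevents an impossible record, so the override should not simply be disabled for imputed starts.

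One could also defend the rule as conservative, since unclear drugs are commonly counted as concomitant. That does not hold here: the recorded stop month already excludes use on Day 1.

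A reader might go further and infer that a prohibited drug stopped before screening, such as systemic cyclosporine, would raise a false protocol deviation. The documents do not support this. Nothing in Protocol 11.4 or SAP 7.3.1 derives deviations from imputed dates, and the exclusion concerns ongoing therapy. SAP 7.2 lists each eCRF module by subject, without saying that imputed dates replace the recorded ones.

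**Conclusion.** The rule is wrong as written, within a narrow pattern: start month missing, start and stop both in the first-dose year, stop month known and before the first-dose month, stop day missing. In that pattern a recorded stop month is always overwritten by an imputed start, and both dates fall on Day 1. No other section repairs it.

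The consequence for classification assumes that imputed dates separate prior from concomitant medication. The consequence for timing assumes that they feed the between-visit summaries. The number of affected records cannot be known from the documents. Only descriptive medication summaries and timing are affected; no efficacy estimate or test uses these dates. The point is minor, but the correction is nearly free.

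**What to change.** Make two changes to the SAP.

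1. **10.2.2.1:** extend the pull-back to partial stop dates. If the imputed start is later than the latest date compatible with the recorded stop month/year, set the start to that latest date. In the worked record this gives start = stop = 31 Mar 2018, before Day 1. It also repairs the earlier-year cases.
2. **10.2.2.2:** keep the rule that moves the stop to the start, imputed or not, but never move a stop beyond its recorded month/year. The October 2019 record then still resolves to start = stop = 1 Oct 2019, which lies within its recorded stop year.

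The cost is two sentences and a small programming change, with no new data.
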